## **12. OTHER ANALYSES**

Not applicable.

## 13. REPORTING CONVENTIONS

Unless stated otherwise, the following reporting conventions will be used. P-values  $\geq 0.001$  and  $\leq 0.999$  will be reported to 3 decimal places; p-values less than 0.001 will be reported as “ $<0.001$ ”. The mean, standard deviation, and other statistics will be reported to 1 decimal place greater than the original data. The minimum and maximum will use the same number of decimal places as the original data. Proportions will be presented as 2 decimal places; values greater than zero but  $<0.01$  will be presented as “ $<0.01$ ”. Percentages will be reported to the nearest whole number; values greater than zero but  $< 1\%$  will be presented as “ $<1$ ”; values greater than 99% but less than 100% will be reported as “ $>99$ ”. Confidence intervals will be reported to the same number of decimal places as the point estimate. Estimated parameters, not on the same scale as raw observations (e.g., regression coefficients) will be reported to 3 significant figures.

## **14. TECHNICAL DETAILS**

SAS version 9.4 or above will be used to generate all tables, figures, and listings.

**15. SUMMARY OF CHANGES IN THE CONDUCT OF THE STUDY OR PLANNED ANALYSES**

- This is a Phase 1 study and is not designed to test any formal statistical hypotheses. As such, the Fisher's Exact tests comparing the rates of solicited and unsolicited AEs between the CJC2 and CJC2+ALFQ groups within a dose cohort have been removed; we are unlikely to gain any useful information from these tests given the small sample sizes and the multiple comparisons that would be introduced.
- After receiving the dose verification results but before database lock and unblinding, additional analyses to look at the correlation between estimated CJC2 dose received and immune responses were added. The added tables are [Table 28](#) and [Table 29](#); the added figures start at [Figure 22](#) and end at [Figure 31](#); additionally, the estimated doses received will be summarized by vaccination and treatment group ([Table 27](#)) and listed by participant for each vaccination ([Listing 1](#)).
- The modified Intention to Treat (mITT) analysis population described in the protocol has been renamed to the “Full Analysis Population” to more accurately describe the population; there are no changes to the definition of what will be included or excluded from this population.

## **17. LISTING OF TABLES, FIGURES, AND LISTINGS**

Table, figure, and listing shells are presented in Appendices 1, 2, and 3.

## 9.1 Overall Study Design and Plan Description

**Table 1: Study Design**

Cohort a	Group b	N	CJCV2 (µg)	ALFQ
1	Sentinel 1-A c	3	1	0
	Sentinel 1-B c	3	1	200 µg 3D-PHAD®, 100 µg QS-21
	1-A	7	1	0
	1-B	7	1	200 µg 3D-PHAD®, 100 µg QS-21
2	Sentinel 2-A c	3	3	0
	Sentinel 2-B c	3	3	200 µg 3D-PHAD®, 100 µg QS-21
	2-A	7	3	0
	2-B	7	3	200 µg 3D-PHAD®, 100 µg QS-21
3	Sentinel 3-A c	3	10	0
	Sentinel 3-B c	3	10	200 µg 3D-PHAD®, 100 µg QS-21
	3-A	7	10	0
	3-B	7	10	200 µg 3D-PHAD®, 100 µg QS-21

Notes: Participants will receive vaccinations on study days 1, 29, and 57.

a SRC Review (PI, Medical Officer, Medical Monitor) through the final vaccine reactogenicity period for each cohort prior to dose escalation.

b Sentinels in each cohort will be randomized 1:1 in a blinded fashion to receive CJCV2 with or without ALFQ. Sentinels will be dosed at least 2 hours apart with no more than 2 sentinels per day.

c SRC Review (PI, Medical Officer, Medical Monitor) 7-9 days after the first dose. SRC review after second and third doses in Sentinel groups will be completed only if a stopping rule is met.

**9.5.1 Immunogenicity and Safety Measurements Assessed and Flow Chart****Table 2: Schedule of Study Procedure**

Study Visit o	00	01	02	03	04	05	06	07	08	09	10	11	12	13	14	15	16	U/S n	E/T
Visit Type- Clinic	x	x		x		x		x		x		x		x	x			x	x
Visit Type, Clinic or Virtual			x		x		x		x		x		x						
Visit Type- Safety Communication q																x	x		
Study Day	-30 to -2	1	3	8	15	29	31	36	43	57	59	64	71	85	113	240	420		
Visit Window n			±1	+1	±2	+2	±1	+1	±2	+2	±1	+1	±2	±2	±4	±7	±7		
Informed Consent a	x																		
Vaccination		x				x				x									
Demographics	x																		
Medical History b	x	x	x	x	x	x	x	x	x	x	x	x	x	x	x			x	x
Concomitant Medication Review c	x	x	x	x	x	x	x	x	x	x	x	x	x	x	x			x	x
Adverse Event Assessment d, e		x	x	x	x	x	x	x	x	x	x	x	x	x	x	x	x	x	x
Counsel on avoidance of pregnancy p	x	x	x	x	x	x	x	x	x	x	x	x	x	x	x				
Physical Exam f	x	x		x		x		x		x		x		x	x			x	x
Vital signs (BP, HR, Temp) g	x	x		x		x		x		x		x		x	x			x	x
Height & Weight	x																x		
Review Eligibility	x	x																	
Urine Pregnancy Test h, i	x	x				x				x				x	x			x	x
Urine Dipstick for protein	x																	x	
Urine Opiate Test	x																	x	
Anti-HIV-1/2, HbsAg, Anti-HCV	x																	x	
HLA-B27	x																		
Hematology & Chemistry j	x			x				x			x			x				x	x
Reactogenicity Assessment k		x				x				x								x	

Study Visit o	00	01	02	03	04	05	06	07	08	09	10	11	12	13	14	15	16	U/S n	E/T
E-Memory Aid l		x	x	x		x	x	x		x	x	x						x	
Study Vaccination Site Examination		x	x	x		x	x	x		x	x	x						x	
Serum (Serology)		x		x		x		x		x		x		x	x			x	x
Blood (PBMCs) for ALS		x		x				x				x						x	
Blood (PBMCs) for Secondary Research		x		x		x		x		x		x		x	x			x	x
Serum for Secondary Research		x		x		x		x		x		x		x	x			x	x
Stool for Secondary Research m		x		x				x				x						x	x
Approx. blood mL by day	37	100		70		40		70		40		70		40	40			40	40

a Prior to study procedures.b Complete medical history will be obtained by interview of participants at the screening visit and will be updated on Day 1 prior to the first study vaccination. Interim medical history will be obtained by interview of participants at follow-up visits after the first study vaccination. Contraception history will be collected for females of childbearing potential.c All current medications and medications taken within 30 days prior to signing the ICF. Concomitant medications taken within 30 days of enrollment through 28 days post last vaccination are collected in Advantage eClinical®.d AEs will be assessed through 28 days post last vaccination. SAEs will be followed throughout the study duration.e Unsolicited AEs including MAAEs, NOCMCs, PIMMCs, and SAEs will be collected from participants throughout their period of study participation and SAE to include concomitant medication(s) taken for these events.f An abbreviated physical examination will be performed at screening. A targeted physical examination may be performed at subsequent visits, if indicated based on review of medical history and any updates obtained by interview of participants.g Participants must not eat or drink anything hot or cold, or smoke within 10 minutes prior to taking oral temperature.h Prior to vaccinationi A urine pregnancy test will be performed within 24 hours prior to study vaccinations and results must be negative and known prior to each study vaccination.j Hematology and Chemistry tests include WBC, Hgb, platelet count, ANC, sodium, potassium, creatinine, T. bili, ALT.k Reactogenicity assessments will occur prior to and  $\geq$  30 minutes post vaccination.l E-memory aid tools and education will be provided on the days of vaccination. E-memory aid review will occur 48 hours and 7 days post vaccination.m Stool kits will be provided during the visits preceding expected stool collection days.n Unscheduled study (U/S) events and Early Termination (E/T) events to occur as indicatedo Visit Window to be initiated at Day 1 of each vaccination day.p Counseling on avoidance of pregnancy will be performed on females of childbearing potential.q Safety Communication follow up visits may occur via phone or email communication

### 9.7.1 Sample Size

**Table 3: Sample Size/Probability Estimates**

N per Treatment Group	No observed AEs 95% CI
10	0-31%

## 10.2 Protocol Deviations

**Table 4: Distribution of Protocol Deviations by Category, Type, and Treatment Group**

*[Implementation Note: Only include categories and deviation types with a count >0. Only include the “Any type” row for a category if there is more than 1 distinct deviation type reported in the category. Only include participant-specific deviations.]*

Category	Deviation Type	1 µg CJCV2 (N=X)		1 µg CJCV2+ALFQ (N=X)		3 µg CJCV2 (N=X)		3 µg CJCV2+ALFQ (N=X)		10 µg CJCV2 (N=X)		10 µg CJCV2+ALFQ (N=X)		All Participants (N=X)	
		n	m	n	m	n	m	n	m	n	m	n	m	n	m
Major Deviations a															
[Category 1]	Any type	x	x	x	x	x	x	x	x	x	x	x	x	x	x
	[Type 1]	x	x	x	x	x	x	x	x	x	x	x	x	x	x
	[Type 2]	x	x	x	x	x	x	x	x	x	x	x	x	x	x
	[Type 3]	x	x	x	x	x	x	x	x	x	x	x	x	x	x
[Category 2]	Any type	x	x	x	x	x	x	x	x	x	x	x	x	x	x
	[Type 1]	x	x	x	x	x	x	x	x	x	x	x	x	x	x
	[Type 2]	x	x	x	x	x	x	x	x	x	x	x	x	x	x
	[Type 3]	x	x	x	x	x	x	x	x	x	x	x	x	x	x
[Category 3]	Any type	x	x	x	x	x	x	x	x	x	x	x	x	x	x
	[Type 1]	x	x	x	x	x	x	x	x	x	x	x	x	x	x
	[Type 2]	x	x	x	x	x	x	x	x	x	x	x	x	x	x
	[Type 3]	x	x	x	x	x	x	x	x	x	x	x	x	x	x
Minor Deviations															
[Category 1]	Any type	x	x	x	x	x	x	x	x	x	x	x	x	x	x
	[Type 1]	x	x	x	x	x	x	x	x	x	x	x	x	x	x
	[Type 2]	x	x	x	x	x	x	x	x	x	x	x	x	x	x
	[Type 3]	x	x	x	x	x	x	x	x	x	x	x	x	x	x
[Category 2]	Any type	x	x	x	x	x	x	x	x	x	x	x	x	x	x

Category	Deviation Type	1 µg CJCV2 (N=X)		1 µg CJCV2+ALFQ (N=X)		3 µg CJCV2 (N=X)		3 µg CJCV2+ALFQ (N=X)		10 µg CJCV2 (N=X)		10 µg CJCV2+ALFQ (N=X)		All Participants (N=X)	
		n	m	n	m	n	m	n	m	n	m	n	m	n	m
[Type 1]	[Type 1]	x	x	x	x	x	x	x	x	x	x	x	x	x	x
	[Type 2]	x	x	x	x	x	x	x	x	x	x	x	x	x	x
	[Type 3]	x	x	x	x	x	x	x	x	x	x	x	x	x	x
[Category 3]	Any type	x	x	x	x	x	x	x	x	x	x	x	x	x	x
	[Type 1]	x	x	x	x	x	x	x	x	x	x	x	x	x	x
	[Type 2]	x	x	x	x	x	x	x	x	x	x	x	x	x	x
	[Type 3]	x	x	x	x	x	x	x	x	x	x	x	x	x	x
All Deviations															
[Category 1]	Any type	x	x	x	x	x	x	x	x	x	x	x	x	x	x
	[Type 1]	x	x	x	x	x	x	x	x	x	x	x	x	x	x
	[Type 2]	x	x	x	x	x	x	x	x	x	x	x	x	x	x
	[Type 3]	x	x	x	x	x	x	x	x	x	x	x	x	x	x
[Category 2]	Any type	x	x	x	x	x	x	x	x	x	x	x	x	x	x
	[Type 1]	x	x	x	x	x	x	x	x	x	x	x	x	x	x
	[Type 2]	x	x	x	x	x	x	x	x	x	x	x	x	x	x
	[Type 3]	x	x	x	x	x	x	x	x	x	x	x	x	x	x

Notes: N = Number of participants enrolled.

n = Number of participants reporting specified deviation; a participant is only counted once per deviation type.

m = Number of deviations.

a A deviation is classified as major if it has the potential to negatively impact the rights, welfare, or safety of the participant or to substantially negatively impact the scientific integrity or validity of the study.

## 12.2.2 Displays of Adverse Events

**Table 5:      Solicited Adverse Event Grading Scale**

Injection Site Reaction	Mild (Grade 1)	Moderate (Grade 2)	Severe (Grade 3)
Pain – experienced without touching the injection site (spontaneous discomfort)	Participant is aware of pain, but it does not interfere with daily activity, and if pain medication is used, it is Over the Counter (OTC) and used for less than 24 hours	Participant is aware of pain; there is interference with daily activity or OTC pain medication is used for more than 24 hours	Participant is aware of pain, and it prevents daily activity or pain requires prescription medication
Tenderness-experienced with touching the injection site	Participant is aware of pain, but it does not interfere with daily activity, and if pain medication is used, it is Over the Counter (OTC) and used for less than 24 hours	Participant is aware of pain; there is interference with daily activity or OTC pain medication is used for more than 24 hours	Participant is aware of pain, and it prevents daily activity or pain requires prescription medication
Ecchymosis (Bruising) a	Does not interfere with daily activity	Interferes with daily activity	Prevents daily activity
Erythema (Redness) a	Does not interfere with daily activity	Interferes with daily activity	Prevents daily activity
Induration (Hardness)/Edema (Swelling) a	Does not interfere with daily activity	Interferes with daily activity	Prevents daily activity
Injection Site Reaction	Small	Medium	Large
Ecchymosis (Bruising) b	<20 mm	20 mm – 50 mm	>50 mm
Erythema (Redness) b	<20 mm	20 mm – 50 mm	>50 mm
Induration (Hardness)/Edema (Swelling) b	<20 mm	20 mm – 50 mm	>50 mm
Systemic	Mild (Grade 1)	Moderate (Grade 2)	Severe (Grade 3)
Feverishness	No interference with daily activity	Some interference with daily activity	Significant interference, prevents daily activity
Fatigue	No interference with daily activity	Some interference with daily activity	Significant interference, prevents daily activity
Malaise	No interference with daily activity	Some interference with daily activity	Significant interference, prevents daily activity
Myalgia c	No interference with daily activity	Some interference with daily activity	Significant interference, prevents daily activity
Arthralgia c	No interference with daily activity	Some interference with daily activity	Significant interference, prevents daily activity

Injection Site Reaction	Mild (Grade 1)	Moderate (Grade 2)	Severe (Grade 3)
Headache	No interference with daily activity	Some interference with daily activity	Significant interference, prevents daily activity or headache requires prescription medication
Nausea	No interference with daily activity	Some interference with daily activity	Significant interference, prevents daily activity or nausea requires prescription medication
Vomiting	No interference with daily activity	Some interference with daily activity	Significant interference, prevents daily activity or vomiting requires prescription medication
Systemic (Quantitative)	Mild (Grade 1)	Moderate (Grade 2)	Severe (Grade 3)
Fever d – oral e	38.0°C – 38.4°C 100.4°F – 101.1°F	38.5°C – 38.9°C 101.2°F – 102.0°F	>38.9°C >102.0°F

Notes:

a Will also be measured in mm but size will not be used as halting criteria.

b Will not be used as halting criteria.

c Not at injection site.

d A fever can be considered not related to the study product if an alternative etiology can be documented.

e Oral temperature assessed on Day 1 prior to the first study vaccination will be considered as baseline. Participants must not eat or drink anything hot or cold, or smoke within 10 minutes prior to taking oral temperature.

**Table 6: Vital Signs Grading Scale**

Measurement	Mild (Grade 1)	Moderate (Grade 2)	Severe (Grade 3)
Tachycardia	101 – 115 bpm	116 – 130 bpm	> 130 bpm or ventricular dysrhythmias
Bradycardia	45 – 49 bpm	40 – 44 bpm	< 40 bpm
Systolic Hypertension	141 – 150 mmHg	151 – 160 mmHg	> 160 mmHg
Systolic Hypotension	85 – 89 mmHg	80 – 84 mmHg	< 80 mmHg
Diastolic Hypertension	91 – 95 mmHg	96 – 100 mmHg	> 100 mmHg
Diastolic Hypotension	50 – 54 mmHg	45 – 49 mmHg	< 45 mmHg
Oral Temperature a	38.0°C – 38.4°C 100.4°F – 101.1°F	38.5°C – 38.9°C 101.2°F – 102.0°F	>38.9°C >102.0°F

Note: Vital signs measurements that meet these grading criteria and represent a worsening of condition from baseline are reported as unsolicited adverse events.

a Oral temperatures assessed from the time of vaccination through 7 days post vaccination for each vaccination will be reported as reactogenicity events rather than as unsolicited adverse events.

**12.4.1 Individual Laboratory Measurements and Abnormal Laboratory Values****Table 7: Laboratory Adverse Event Grading Scale**

Laboratory	Mild (Grade 1)	Moderate (Grade 2)	Severe (Grade 3)
Sodium, low, mEq/L	132 – 135	130 – 131	<130
Sodium, high, mEq/L	146 – 147	148 – 149	150 or greater
Potassium, high, mEq/L	5.2 – 5.3	5.4 – 5.5	>5.5
Potassium, low, mEq/L	3.3 – 3.4	3.1 – 3.2	<3.1
Creatinine, high mg/dL (female)	1.0 - 1.1	1.2 – 2.0	>2
Creatinine, high mg/dL (male)	1.2 - 1.3	1.4 – 2.0	>2
Liver Function Tests (ALT) increase by factor	>1.0-2.5 x ULN	>2.5-5.0 x ULN	>5.0 x ULN
Total bilirubin	>1.0-1.5 x ULN	>1.5-2.0 x ULN	>2.0 x ULN
Hgb (female), low g/dL	10.9 - 11.6	9.4 - 10.8	≤9.3
Hgb (male), low g/dL	13.1 - 13.2	12.5 - 13.0	≤12.4
WBC, increase, cells, $\times 10^3$ u/L	>11.1 - ≤15.0	>15 - ≤20	>20.0
WBC, decrease, cells, $\times 10^3$ u/L	2.5 - <4.4	1.5 - <2.5	<1.5
ANC, $\times 10^3$ u/L	1.2 - <1.7	0.9 - <1.2	<0.9
Platelets, decrease, cells/mm 	124,000-<134,000	100,000<124,000	<100,000
Urine protein	Trace	1+	2+

Note: ULN is the upper limit of the normal range.

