4.1 Eligibility Criteria

4.1.1 Subject Inclusion Criteria

1. Provide informed consent prior to initiation of any study procedures.
2. Able to understand and comply with planned study procedures and be available for all study visits/safety communications.
3. Non-pregnant/non-lactating subjects 18-50 years of age inclusive upon enrollment.
4. In general, good health* to be safely enrolled in this study as determined by medical history, medication use**, and physical exam.

*Good health is defined by the absence of any exclusionary medical conditions. If the subject has another current, ongoing medical condition, the condition cannot meet any of the following criteria: 1) first diagnosed within 3 months of enrollment; 2) is worsening in terms of clinical outcome in last 6 months; or 3) involves need for medication that may pose a risk to subject's safety or impede assessment of AEs or immunogenicity if they participate in the study.

** Topical, nasal, and inhaled medications (except for inhaled corticosteroids as outlined in the Subject Exclusion #17). Herbals, vitamins, and supplements are permitted.

5. Oral temperature is less than 100.4°F.
6. Pulse is 50 to 100 beats per minute (bpm), inclusive.
7. Systolic blood pressure (BP) is 90 to 140 mmHg, inclusive.
8. Diastolic BP is 55 to 90 mmHg, inclusive.
9. Body Mass Index (BMI) less than 40.

10. Females of childbearing potential* may enroll if subject has practiced adequate contraception** > 30 days prior to enrollment and agrees to continue adequate contraception for the entire study.

* Child-bearing potential is defined as not sterilized via tubal ligation, bilateral oophorectomy, salpingectomy, hysterectomy, or successful Essure® placement (permanent, non-surgical, non-hormonal sterilization) with documented radiological confirmation test at least 90 days after the procedure, and still menstruating or <1 year of the last menses if menopausal.

** Adequate contraception includes non-male sexual relationships, abstinence from sexual intercourse with a male partner, monogamous relationship with vasectomized partner who has been vasectomized for 180 days or more prior to the subject receiving the first study vaccination, barrier methods such as condoms or diaphragms with spermicide, effective intrauterine devices, NuvaRing®, and licensed hormonal methods such as implants, injectables, or oral contraceptives (“the pill”).

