### 3.3. Study Definitions and Derived Variables

Unless otherwise specified, the baseline value will be defined as the last value obtained prior to the first vaccination. Vital signs assessed on Day 1 prior to study vaccination will be considered as baseline. Any medical condition that is present at the time that the participant is screened will be considered as baseline and will only be reported as an AE if symptoms related to the condition occur with greater frequency and/or severity after vaccination during the AE reporting period.

Change from baseline is defined as the additive change from baseline, i.e.,  $CHG_{ij} = y_{ij} - y_{i0}$  where  $y_{ij}$  is the measurement for participant  $i$  at time point  $j$  and  $y_{i0}$  is the measurement for participant  $i$  at baseline (prior to vaccination 1).

Fold-rise (FR) from baseline is defined as the multiplicative change from baseline, i.e.,  $FR_{ij} = \frac{y_{ij}}{y_{i0}}$  where  $y_{ij}$  is the response for participant  $i$  at time point  $j$  and  $y_{i0}$  is the response for participant  $i$  at baseline (pre-vaccination 1). Individual FR values will be reported to 1 decimal place.

The peak titer and peak fold-rise are defined as the maximum value for a participant at any time after the first vaccination.

A responder is defined as having  $\geq 4$ -fold increase relative to baseline, i.e.,  $FR_{ij} \geq 4$  for participant  $i$  at post-baseline time point  $j$ . For serum assays, participants are classified as responders or not at Days 8, 29, 36, 57, 64, 85, and 113; for the ALS assay, participants are classified as responders or not at Days 8, 36, and 64.

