## Vital Signs

Per the MOP Appendix B, vital signs that meet the protocol-defined toxicity grading scale ([Table 6](#)) and represent a worsening condition from baseline are reported as an unsolicited AE with the exception of temperatures collected from the time of vaccination through 7 days post vaccination for each vaccination which will be reported as solicited AEs.

The last measurement prior to receiving the first vaccination for each parameter will be considered baseline.

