## 14.3 Safety Data

### 14.3.1 Displays of Adverse Events

**Table 30: Overall Summary of Adverse Events**

*[Implementation Note: For the severity rows, a participant will only be counted in one severity category and will be categorized by the maximum severity experienced.]*

	1 µg CJCV2 (N=X)		1 µg CJCV2+ALFQ (N=X)		3 µg CJCV2 (N=X)		3 µg CJCV2+ALFQ (N=X)		10 µg CJCV2 (N=X)		10 µg CJCV2+ALFQ (N=X)		All Participants (N=X)	
Participants with	n	%	n	%	n	%	n	%	n	%	n	%	n	%
At least one local solicited adverse event a	x	x	x	x	x	x	x	x	x	x	x	x	x	x
At least one systemic solicited adverse event a	x	x	x	x	x	x	x	x	x	x	x	x	x	x
At least one unsolicited adverse event b	x	x	x	x	x	x	x	x	x	x	x	x	x	x
Mild (Grade 1)	x	x	x	x	x	x	x	x	x	x	x	x	x	x
Moderate (Grade 2)	x	x	x	x	x	x	x	x	x	x	x	x	x	x
Severe (Grade 3)	x	x	x	x	x	x	x	x	x	x	x	x	x	x
At least one related unsolicited adverse event b	x	x	x	x	x	x	x	x	x	x	x	x	x	x
Mild (Grade 1)	x	x	x	x	x	x	x	x	x	x	x	x	x	x
Moderate (Grade 2)	x	x	x	x	x	x	x	x	x	x	x	x	x	x
Severe (Grade 3)	x	x	x	x	x	x	x	x	x	x	x	x	x	x
At least one clinical laboratory adverse event a	x	x	x	x	x	x	x	x	x	x	x	x	x	x
At least one related clinical laboratory adverse event a	x	x	x	x	x	x	x	x	x	x	x	x	x	x
At least one serious adverse event c,d	x	x	x	x	x	x	x	x	x	x	x	x	x	x

	1 µg CJCV2 (N=X)		1 µg CJCV2+ALFQ (N=X)		3 µg CJCV2 (N=X)		3 µg CJCV2+ALFQ (N=X)		10 µg CJCV2 (N=X)		10 µg CJCV2+ALFQ (N=X)		All Participants (N=X)	
Participants with	n	%	n	%	n	%	n	%	n	%	n	%	n	%
At least one related, serious adverse event c,d	x	x	x	x	x	x	x	x	x	x	x	x	x	x
At least one adverse event leading to early termination e	x	x	x	x	x	x	x	x	x	x	x	x	x	x
At least one medically attended adverse event d	x	x	x	x	x	x	x	x	x	x	x	x	x	x
At least one new onset chronic medical condition d	x	x	x	x	x	x	x	x	x	x	x	x	x	x
At least one potentially immune mediated medical condition d	x	x	x	x	x	x	x	x	x	x	x	x	x	x

Notes: N = Number of participants in the Safety Population.

Participants can only be counted once for each category regardless of the number of events and are categorized by maximum severity.

a Collected from vaccination through 7 days post vaccination for each vaccination.

b Collected from vaccination through 28 days post vaccination for each vaccination.

c A listing of Serious Adverse Events is included in Section 14.3.2.

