d Collected from the time of first vaccination through 12 months following final vaccination.

e As reported on the Adverse Event eCRF.

**Table 31: Non-Serious Adverse Events Occurring in At Least 5% of Participants in Any Treatment Group and All Serious Adverse Events by MedDRA System Organ Class and Preferred Term and Treatment Group**

*[Implementation Note: This table is used to complete the “Other Adverse Event Template” for clinicaltrials.gov reporting. Solicited AEs, unsolicited AEs, and laboratory AEs should be considered for inclusion in this table. Solicited and unsolicited AEs will be considered separately when determining whether the AE meets the 5% criterion and will be reported in separate rows. Solicited AEs (reported on the Treatment Administration Record, Solicited Events Record, or Vital Signs [only temperature within solicited event reporting period] forms) and protocol-defined laboratory parameters (reported on the Local Laboratory Results form) will be included in the systematic collection rows. Any non-serious AEs reported on the Adverse Event form (including graded vital signs and non-protocol defined laboratory parameters) will be included in the non-systematic collection rows. All SAEs should be included in the table, i.e., the 5% criterion does not need to be met for the event to be included in the table. For SAEs and non-serious AEs that were non-systematically collected, an event is defined by each eCRF submitted. For AEs that were systematically collected, an event is defined by occurrence after a single vaccination, i.e., a single participant who received all three vaccinations could contribute up to three events for each symptom/parameter collected. Sort the SOCs by descending incidence (n) and frequency (Events) across all participants (any other ties should be in alphabetical order). Within an SOC, sort the PTs by descending incidence (n) and frequency (Events) across all participants (any other ties should be in alphabetical order).]*

Preferred Term	MedDRA System Organ Class	1 µg CJC2 (N=X)			1 µg CJC2+ALFQ (N=X)			3 µg CJC2 (N=X)			3 µg CJC2+ALFQ (N=X)			10 µg CJC2 (N=X)			10 µg CJC2+ALFQ (N=X)			All Participants (N=X)				
		n	%	Events	n	%	Events	n	%	Events	n	%	Events	n	%	Events	n	%	Events	n	%	Events	n	%
Serious Adverse Events a																								
All	All	x	x	x	x	x	x	x	x	x	x	x	x	x	x	x	x	x	x	x	x	x	x	x
[PT 1]	[SOC 1]	x	x	x	x	x	x	x	x	x	x	x	x	x	x	x	x	x	x	x	x	x	x	x

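### Grade 1 vital-sign cut-offs start one unit outside the entry limits, so ordinary variation adds events to the all-causality unsolicited-AE rates, and Cohort 1 had twice as many scheduled readings

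*SAP*

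**What the plan says.** Entry limits are in Protocol 4.1.1: "Pulse is 50 to 100 beats per minute (bpm), inclusive"; "Systolic blood pressure (BP) is 90 to 140 mmHg, inclusive"; "Diastolic BP is 55 to 90 mmHg, inclusive". They are checked again before the first dose (Protocol 5.2), and SAP 3.3 makes that reading the reference: "Vital signs assessed on Day 1 prior to study vaccination will be considered as baseline".

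SAP Table 6 starts Grade 1 at 101 and 49 bpm, 141 and 89 mmHg systolic, and 91 and 54 mmHg diastolic. Its note gives the reporting rule: "Vital signs measurements that meet these grading criteria and represent a worsening of condition from baseline are reported as unsolicited adverse events". The vital-signs paragraph of SAP 4.5.1 attributes the rule to a document outside the public set: "Per the MOP Appendix B, vital signs that meet the protocol-defined toxicity grading scale".

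These events then reach the unsolicited-AE tables. The implementation note to Table 31 describes the non-systematic rows as "Any non-serious AEs reported on the Adverse Event form (including graded vital signs and non-protocol defined laboratory parameters". Table 30 has the row "At least one unsolicited adverse event", and SAP 9.3.2 gives that proportion with a 95% CI by arm in Tables 47-49.

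SAP 9.7 schedules post-baseline vital signs for all cohorts on Days 8, 29, 36, 57, 64, 85 and 113. Cohort 1, under protocol v4.0, also had them on Days 3, 15, 31, 43, 59 and 71. Unsolicited AEs are collected to 28 days after the last dose, about Day 85.

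**The concern.** A participant eligible on Day 1 has a baseline inside all six limits. Any later reading that earns a grade is outside a limit, and so is already worse than baseline in that direction. The worsening condition therefore screens out nothing. A participant with a systolic pressure of 140 at baseline and 141 at one later visit has a Mild unsolicited AE under the text as written.

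The trial has no placebo arm (SAP 4.2), so background events cannot be subtracted from a dose group's unsolicited-AE rate. With 10 participants per arm, one person is 10%, which already exceeds the 5% display threshold of Table 31. The number of chances to cross a cut-off also differs by dose: 12 scheduled readings in the AE window at 1 µg, 6 at 3 µg and 10 µg. A reader comparing the all-causality rate across doses would be comparing unequal ascertainment, and a real dose trend could be masked or distorted.

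**Working it through.** **The plan's own figure.** The only related number is the interval for 0 events in 10 (SAP 5). Clopper-Pearson upper limit: 1 − 0.025^(1/10) = 0.3085, so 0-31% is reproduced. No expected rate of vital-sign events is stated.

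**The gap at each limit.**
- Pulse: 101 − 100 = 1; 50 − 49 = 1.
- Systolic: 141 − 140 = 1; 90 − 89 = 1.
- Diastolic: 91 − 90 = 1; 55 − 54 = 1.

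**Readings in the AE window.** Cohorts 2-3: Days 8, 29, 36, 57, 64, 85 = 6. Cohort 1: those 6 plus Days 3, 15, 31, 43, 59, 71 = 12. Day 113 falls outside. SAP 4.3 lists the major eligibility changes between protocol versions and the vital-sign limits are not among them, so I use the same limits for Cohort 1.

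**Simulation with no vaccine effect.** Each reading is a person's own mean plus independent visit error, both normal, rounded to whole units. Screening and Day 1 must both meet the entry limits. An event is any later reading outside a limit. Temperature is left out. All means and SDs are assumptions, in the order systolic/diastolic/pulse. Set A takes the three signs as uncorrelated, with means 120/75/72 and between-person SD 11/8/9. Set B lets the means rise with the SD (114/70/68, 116/72/70, 118/74/72, 120/76/72), uses between-person SD 9-11/6-8/8-10, and sets the systolic-diastolic correlation at 0.6.

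| Set | Within-person SD | 6 readings | 12 readings |
|---|---|---|---|
| A | 5/4/5 | 18% | 26% |
| A | 7/5/6 | 29% | 42% |
| A | 9/7/8 | 50% | 69% |
| B | 5/4/5 | 12% | 18% |
| B | 6/5/6 | 20% | 31% |
| B | 8/6/7 | 34% | 49% |
| B | 9/7/8 | 48% | 66% |

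**Per 10-person arm.** Expected participants with at least one event: 10 × 0.12 = 1.2 to 10 × 0.50 = 5.0 over 6 readings; 10 × 0.18 = 1.8 to 10 × 0.69 = 6.9 over 12. Even at 12%, the chance of at least one in an arm is 1 − 0.88^10 = 72%.

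**Effect of the extra visits.** At equal variability, the step from 6 to 12 readings adds 18 − 12 = 6 points at the low end and 69 − 50 = 19 at the high end.

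**Check needing no SD.** If P is the share over 6 readings and visits are independent within a person, the share over 12 is at most 1 − (1 − P)², because events cluster in the same people. For P = 12%, 29% and 50% the ceiling is 23%, 50% and 75%. The simulated 18%, 42% and 69% lie below it, as they should.

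**The case against.** Several points on the other side stand.

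- **The percentages are not facts about this trial.** The documents give no mean or SD. A reader might take one range, such as 18-50%, as established; it is one set of assumptions at 6 readings and does not describe Cohort 1.
- **Confirmation may exist.** A reader might infer that no repeat reading is required. The SAP refers to the manual's Appendix B, so the absence can be asserted only of the protocol and SAP.
- **The primary endpoint is narrower.** It counts vaccine-related unsolicited AEs (SAP 3.2), judged by clinicians blinded to ALFQ. A reader might infer that an inert product would look harmful. That would need stray readings to be judged related, and nothing in the documents shows they would be.
- **The adjuvant comparison is randomised within cohort.** Both arms have the same schedule and cut-offs, so the noise blurs that contrast without biasing it.
- **Much separation is already planned.** Tables 47-61 are by SOC and preferred term, Table 30 has grade and related rows, Tables 89-93 show graded vital signs by visit, and Listing 14 gives every reading. Clinical events are therefore not hidden; the mixing is confined to the totals.

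The last point does not dispose of the matter. Someone may have both a vital-sign event and another AE, so participant counts cannot be subtracted, and no planned table gives the share with an unsolicited AE other than a vital sign. Table 30 does give laboratory AEs their own rows.

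A tempting remedy is to count only abnormalities present at two consecutive scheduled visits. It would be unsafe for drawing conclusions. In Cohorts 2-3 each adjacent pair joins a reading 7 days after a dose to one about 28 days after a dose, so a transient effect would rarely be confirmed. In set A with SD 7/5/6, an assumed +15 mmHg systolic effect at each 7-day visit raises the any-visit share from 29% to about 59%, but the two-visit share only from 5% to 9%.

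**Conclusion.** The concern holds for the all-causality unsolicited-AE totals: Table 30 and the any-SOC rows of Tables 47-49. The one-unit gap, the ineffective worsening condition and the 12-versus-6 schedule come directly from the documents. The size does not: about 12-50% of participants over 6 readings and 18-69% over 12 rests on assumed means and SDs, normal variation, independent visit errors, and no repeat-reading rule in the manual. If the manual requires confirmation, the rates would be lower.

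The consequence is limited. The main problem is comparison across doses, where Cohort 1's extra readings could add roughly 6 to 19 percentage points. The documents do not support reading this as a bias in the adjuvant contrast or as a general inflation of the primary endpoint. This is a cheap improvement to reporting, not a flaw that undermines the safety analysis.

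**What to change.** In Table 30 and the any-SOC rows of Tables 47-49, keep the existing total and add two sub-rows: (a) participants with at least one unsolicited AE other than a graded vital sign; (b) participants whose only unsolicited AEs are graded vital signs. The two are exclusive and sum to the total, which gives a programming check.

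Base any cross-dose comparison of unsolicited AEs on (a). Show (b) a second time restricted to the visits common to all cohorts (Days 8, 29, 36, 57, 64, 85), and footnote that Cohort 1 had 12 scheduled readings in the AE window against 6 in Cohorts 2-3. Do not use a two-consecutive-visit filter to draw conclusions. Keep every event in Listing 11. If the manual's Appendix B specifies a repeat reading, state it in the SAP.

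Protocol 5.3.1 still lists vital signs, as applicable, at the 3- and 15-day visits while Appendix A does not; the two should be reconciled.

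The cost is a change to table shells and some programming on data already collected. No grading or clinical rule changes. The downside is a few extra rows.
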